5.1 Variables

LML134 plasma concentration will be the PK variable of interest for this study. Conventional PK parameters will not be calculated by noncompartmental analysis due to the limited sampling schedule. The data will be part of the overall Population PK model.

5.2 Descriptive analyses

LML134 plasma concentration data will be listed by treatment, subject, and sampling time point. Descriptive summary statistics will be provided by treatment and sampling time point. Summary statistics will include mean (arithmetic and geometric), SD, CV (arithmetic and geometric), median, minimum, maximum, and the frequency (n, %) of concentrations below the LLOQ. Concentrations below LLOQ will be treated as zero in summary statistics. A geometric mean will not be reported if the dataset includes zero values.

Graphical methods will be employed to show mean and individual concentration-time profiles. For the plots, time will be defined as the hours post first-dose within each period.

6 Statistical methods for Pharmacodynamic (PD) parameters

All subjects within the full analysis set will be included in the PD data analysis.

6.1 Primary objective

The primary objective of this study is to demonstrate that wakefulness in shift work disorder (SWD) patients is significantly increased after treatment with LML134 compared to placebo.

6.1.1 Variables

The mean of multiple sleep latency test (MSLT) scores is the primary variable of this study.

Each subject will undergo a sleep latency test assessment at each period, at approximately 1:30, 3:30, 5:30 and 7:30 in Day 2 (Night 1) and Day 3 (Night 2) during Treatment Period 1 and same time points in Days 12 and 13 in Treatment Period 2. In total, a subject will have 8 sleep latency test assessments in each treatment period. The mean value of all the sleep latencies from a subject within a period will be defined as mean sleep latency score for that subject for that period.

No change from baseline comparison will be used as no baseline is collected due to the short duration of the study.

6.1.2 Descriptive analyses

The primary variable will be listed by treatment sequence, patient and period, and descriptive statistics will be provided by treatment. Summary statistics will include mean (arithmetic and geometric), SD, CV (arithmetic and geometric), median, minimum, maximum.

Boxplots will be employed to present the MSLT results by treatment.

6.1.3 Statistical model, assumptions and hypotheses

MSLT from both periods will be included in the analysis.

Corporate Confidential Information

Due to high variability and time difference between screening MSLT and post treatment records, screening MSLT will not be used as a covariate for modelling. Total sleep time from sleep diary data during baseline will be used as baseline covariate. Therefore both smoking status (nicotine intake) and total sleep time at baseline will be considered as covariates in the model.

The primary variable, mean MSLT of a subject within a period, will be analyzed using a mixed effect analysis of variance model. This model will have the mean MSLT as the dependent variable; treatment, actual treatment sequence, smoking status at screening, total sleep time at baseline, treatment interaction with total sleep time at baseline and smoking status and period as fixed effects and a subject level random intercept. Primary analysis will be assessed over full analysis set.

Least square estimates for each treatment (LML134 and placebo) and treatment difference (LML134 vs placebo) along with 95% confidence interval will be reported.

The following assessments will be performed to judge efficacy of LML134:

1. Statistical significance: One sided (superiority) p-value of LML134 vs placebo from above fitted ANOVA model will be reported.

A p-value < 0.1 will be considered as a positive sign for statistical significance.

2. Estimate of treatment difference (LML134 vs Placebo) will be reported.
An estimate of treatment difference > 1 minute would be considered as significant.

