11.4.2 Statistical model, hypothesis, and method of analysis

Nicotine is a powerful substance to stimulate wakefulness and attention. At same time screening MSLT reflects the stage of severity of shift work disorder patients. Therefore both smoking status (/nicotine intake) and MSLT at screening will be considered as covariates in the model.

For statistical analysis purposes; subjects under full analysis set with all available MSLT information from both the periods will be included in the analysis.

Mean sleep latency score data will be analyzed using a mixed effect ANOVA model with treatment smoking status at screening, screening MSLT, treatment interaction with screening MSLT and smoking status and period as fixed effects and subject as a random effect. Least square estimates for each treatment and treatment difference (LML134 vs placebo) along with 95% confidence interval will be reported. In studies with short treatment duration in SWD patients or healthy shift workers the usual approach is to compare post-dose conditions and not change from baseline. The reason for this approach is the high variability in MSLT (average of at least three tests is needed as baseline) and that baseline and post-dose MSLT results need to be time matched, as MSLT results depend on circadian rhythm.

The following assessments will be performed to judge efficacy of LML134:

a. Statistical significance: One sided (superiority) p-value of LML134 vs placebo from above fitted ANOVA model will be reported.

A p-value <0.1 will be considered as a positive sign for statistical significance.

b. Estimate of treatment difference (LML134 vs Placebo) will be reported.

An estimate of treatment difference > 1 minute would be considered as significant.

In addition from the above model, effect of LML over placebo in each subgroup (smoking status and MSLT (<6 and ≥ 6)) will be estimated through 95% CI of interaction effects.

Same analysis will be performed at interim.

Graphical display:

Subjects under safety analysis set will be used for reporting. For a thorough investigation of sleep latency time profiles, data from LML134 and placebo will be superimposed using suitable graphical tools like boxplot or arithmetic mean (SD) statistics.

Descriptive summary:

Subjects under safety analysis set will be used for reporting. Sleep latency data will be summarized by treatment and time point. Summary statistics like N, mean, SD, CV, and range will be reported.

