11.4.4 Sensitivity analyses

Mean of multiple sleep latency score is essentially a positive outcome. Thus a supportive analysis will be performed using log transformed mean sleep latency scores. Log transformed mean sleep latency score data will be analyzed using a mixed effect ANOVA model with treatment and period as fixed effects and subject as a random effect. Least square estimates for each treatment and treatment difference (LML134 vs placebo) along with 95% confidence interval will be back transformed to report in original scale.

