11.7 Sample size calculation

It is planned to have data for 36 subjects with evaluable results under the primary endpoint without any major protocol deviations. Assuming a 20% drop-out rate we expect to enroll approximately 46 subjects. In case there will be less than 36 evaluable subjects additional subjects may be enrolled.

Based on [Czeisler et al 2005](#) a 2 minute increase in primary endpoint for SWD patients compared to placebo is considered to be the ‘true effect’. Furthermore a SD of 4 minutes and a 20% drop out rate is used based on other sleep disorder study experience.

Efficacy criteria:

- a. Statistical significance: A significant increase compared to placebo in sleep latency characterized by p-value < 0.1

And

- b. At least 1 minute increase in MSLT sleep latency compared to placebo characterized by an estimated mean difference of > 1 minute

Sample size is evaluated based on a simulation exercise with an ANOVA model with treatment and period as fixed effects. The following operating characteristics are observed:

Table 11-1 Operating characteristics for dual criteria

True effect* (in mins)	Both criteria met (%)	Both criteria failed (%)	One of the criteria met (%)
1.0	41.3	50.0	8.7
1.2	49.7	41.6	8.7
1.5	62.2	29.8	8.0
1.7	69.9	22.9	7.2
2.0	80.0	14.4	5.6
2.2	85.4	10.2	4.5
2.5	91.5	5.6	2.9

* True effect: Change in MSLT (LML134X-Placebo)

Futility Analysis:

An interim analysis is planned at mid-way with 18 completers to evaluate the chance of attaining proof of concept at the end of the trial. A very low chance may result in early stoppage of the trial due to futility.

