1.4 Study design and treatment

This is a randomized, subject and investigator-blinded, placebo controlled, crossover, multi-center Proof of Concept (PoC) study with in-house simulated laboratory night shifts in patients with SWD.

This non-confirmatory study will include two treatment arms: LML134 and placebo. The study will utilize a 2x2 crossover design, with two treatment periods and two sequences as shown in [Figure 1-1](#) whereas assessment details are shown in [Figure 1-2](#).

Approximately 46 subjects were planned to be randomized in this study (to achieve 36 completers). All subjects will receive both treatments (LML134 and placebo), one in each treatment period, with the order of treatment being randomized. The study is prematurely terminated based on business decision after 18 completers.

Figure 1-1 Study Design

2 First interpretable results (FIR)

No first interpretable result (FIR) is planned for this study. All the results will be represented in clinical study report (CSR).

4 Statistical methods: Analysis sets

For all analysis sets, subjects will be analysed according to the actual study treatment(s) received. This is due to fact that it is known that a few subjects has been mis-randomized to a different treatment group as compared to the planned list of randomization. In order to make use of full data , all analysis will be performed on actual treatment group received by subject instead of a planned one.

The full analysis set will include all subjects that received any study drug and had any post-baseline assessment.

The safety analysis set will include all subjects that received any study drug.

The PK analysis set will include all subjects with at least one available valid (i.e. not flagged for exclusion) PK concentration measurement, who received any study drug and with no protocol deviations that impact on PK data.

For subjects for which the actual treatment received does not match the randomized treatment the treatment actually received will be used for the analysis.

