6.1.3.2 Sensitivity analyses

Mean of multiple sleep latency test (MSLT) score is essentially a positive outcome. Thus, a supportive analysis will be performed using log transformed mean sleep latency scores. Log transformed mean sleep latency score data will be analysed using a mixed effect ANOVA model with treatment, actual treatment sequence, smoking status at screening, total sleep time at baseline treatment interaction with total sleep time at baseline and smoking status and period as fixed effects and subject as a random effect. Geometric means of each treatment and their ratio (LML134 vs placebo) along with 95% confidence intervals will be estimated using least square means by back transforming to the original scale.

A supportive analysis with may be performed with additional covariates (total sleep time on actigraphy during baseline, key PSG parameters at screening/baseline) that may potentially affect individual mean MSLT data.

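### Both efficacy criteria come from a model with a treatment-by-smoking interaction and no stated LS-mean weights, which can inflate the SE and shift the estimate

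*SAP*

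**What the plan says.** SAP 6.1.3 sets one mixed model for each subject's mean MSLT latency per period. It has treatment, actual sequence, smoking status and baseline total sleep time, followed by "treatment interaction with total sleep time at baseline and smoking status and period as fixed effects and a subject level random intercept". From that model, "Least square estimates for each treatment (LML134 and placebo) and treatment difference (LML134 vs placebo) along with 95% confidence interval will be reported".

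Two criteria then judge efficacy. For the first, "One sided (superiority) p-value of LML134 vs placebo from above fitted ANOVA model will be reported", with 0.1 as the limit. The second is an estimated difference above 1 minute. Protocol 11.7 joins the two with an And. The visible text of both documents gives no LS-mean weights for smoking status and no sleep-time value at which the difference is evaluated.

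Related text:
- Protocol 11.4.2 already had the treatment-by-smoking interaction, and used it to estimate the "effect of LML over placebo in each subgroup (smoking status and MSLT" below 6 or at least 6).
- Protocol 11.4.4 had a log-scale sensitivity analysis by a "mixed effect ANOVA model with treatment and period as fixed effects and subject as a random effect". SAP 6.1.3.2 now lists the same interactions as the primary model, ending "and smoking status and period as fixed effects and subject as a random effect".
- Protocol 11.7 based the sample size on a "simulation exercise with an ANOVA model with treatment and period as fixed effects".
- SAP 1.4 reports: "The study is prematurely terminated based on business decision after 18 completers".

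**The concern.** Once treatment interacts with a factor, the overall treatment difference is not defined until the weights for the factor's levels are fixed. The usual LS-mean convention weights levels equally. With two levels, the estimate is then the plain average of the smoker and non-smoker effects, not the average over enrolled patients. With 4 smokers of 18, each smoker has weight 0.5/4 and each non-smoker 0.5/14, a ratio of 3.5.

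Two things are at stake. The estimate loses precision that a study cut to half its planned 36 evaluable subjects can hardly spare. If the drug effect differs by smoking status, the estimate also moves relative to the 1-minute threshold. The interactions serve the protocol's subgroup estimates, and that purpose does not require the decision contrast to come from the same model.

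**Working it through.** **Inputs.** From protocol 11.7: SD 4 minutes, true effect 2 minutes, 36 planned evaluable subjects. From SAP 6.1.3: one-sided 0.1 and estimate > 1 minute. From SAP 1.4: 18 completers. From protocol 6.2: 1:1 sequences. The number of smokers, k, is not in the documents and is varied. Exclusion 10 bars heavy smokers and admits light ones, which does not bound the share.

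**1. Reproduce Table 11-1.** Take SD 4 per period with no within-subject correlation, so the difference has variance 2 × 4² = 32.
- SE = 4 × √(2/36) = 0.943.
- Both criteria are met if the estimate exceeds max(1, 1.2816 × 0.943) = 1.208.
- At a true 2 minutes the chance is 79.9%, against 80.0% stated. All rows agree to within 0.1 point.
- Reading SD 4 as the SD of the difference gives 93.3%, and a two-sided 0.1 gives 68.3%. Neither fits.

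**2. Closed form for the weighting.** Leave out sleep time and assume smoking is balanced over sequences.
- Observed proportions: variance = 32/n. At n = 18, SE = 1.333.
- Equal weights: variance = (32/4) × (1/k + 1/(n − k)).
- SE ratio = n / (2√(k(n − k))).
- k = 7: 18/(2√77) = 1.026. k = 4: 18/(2√56) = 1.203. k = 2: 18/(2√32) = 1.591.

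**3. Full SAP model.** GLS variance with 18 complete pairs, 9 per sequence, within-subject SD 4 and between-subject SD 3. Smokers are placed at random over sequences. Sleep time is period-specific (assumed mean 6 h, between-subject SD 0.8, within-subject SD 0.7). SEs are averaged over simulated designs. The chance of meeting both criteria is at a true 2 minutes, using t with 14 df (15 without interactions).

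| Model and smokers of 18 | SE | Ratio | Difference needed for p < 0.1 (min) | Both criteria met |
|---|---|---|---|---|
| No interactions | 1.35 | 1.00 | 1.81 | 56% |
| SAP, equal weights, 9 | 1.35 | 1.00 | 1.82 | 56% |
| SAP, equal weights, 7 | 1.40 | 1.03 | 1.87 | 54% |
| SAP, equal weights, 6 | 1.45 | 1.07 | 1.94 | 52% |
| SAP, equal weights, 4 | 1.66 | 1.23 | 2.24 | 45% |
| SAP, equal weights, 3 | 1.86 | 1.38 | 2.52 | 40% |
| SAP, equal weights, 2 | 2.23 | 1.65 | 3.00 | 34% |

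The SAP model with observed margins gives SE 1.35 for every k. The ratios exceed the closed form because smoking is not balanced over sequences and sleep time is in the model. The smoking interaction causes the loss: alone, with equal weights, it gives SE 1.64 (k = 4) and 2.19 (k = 2). The sleep-time interaction alone, evaluated at its mean, gives 1.352 against 1.351.

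**4. Shift of the estimate.** If the two effects differ by D, equal weighting moves the estimate by (0.5 − k/18) × D. For an assumed D of 2 minutes:
- k = 7: 0.111 × 2 = 0.22 min.
- k = 4: 0.278 × 2 = 0.56 min.
- k = 2: 0.389 × 2 = 0.78 min.

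Example: with 2 minutes in 14 non-smokers and 0 in 4 smokers, equal weights give 1.0 and observed margins give (14 × 2)/18 = 1.56. The first fails the > 1 minute criterion and the second passes.

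**The case against.** The SAP never says equal weights. Observed margins fit its wording equally well, and a blacked-out block stands in 6.1.3, so what is shown may be an unstated detail. That is fair as far as it goes. However, the sentences on the model and the estimates are intact, and they leave the decision statistic open.

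The two-level coding is inferred, since both documents pair smoking status with nicotine intake. A continuous intake evaluated at its mean would remove the problem. Three levels would not: equal weights would still ignore how many subjects each level holds. Protocol 11.4.2 treats smoking status as a subgroup, which favours a factor.

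The size is assumed. With 6 to 9 smokers the loss is at most 7% in SE and 4 points of probability, and the 65% needs only 2 smokers. The needed difference passes 2 minutes only at 4 or fewer smokers in the table and at SD 4; at SD 3 the 2.24 becomes 1.68. The two harms also differ in premise: the shift needs unequal effects, and a 2-minute gap is as large as the whole assumed drug effect. All of this stands, and it limits the size rather than the point.

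The descriptive summaries (SAP 6.1.2) and the secondary repeated-measures model (6.2.3), which has no covariate interactions, give a partial cross-check. Neither is tied to the criteria.

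Finally, dropping the interactions departs from the protocol's primary model after the trial stopped. That is a reason to document the change or to prefer the observed-margins option. The SAP has itself already replaced screening MSLT by sleep time in that model.

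**Conclusion.** The point holds and should be fixed. As visible, SAP 6.1.3 does not fix the weights behind its two efficacy criteria. Under conventional equal-weight LS means with two-level smoking status, the SE rises by about 3%, 23% or 65% for 7, 4 or 2 smokers of 18 (2.6%, 20% and 59% by the closed form), and not at all near an even split. Most of the fall from the planned 80% comes from stopping at 18; the model choice costs a further 0 to 22 points (56% down to 34%).

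The figures rest on assumed smoker counts, SD 4 in both models and 18 complete pairs. A real interaction would lower the residual SD in the SAP model, and full-analysis-set subjects with one period are left out. Confidence is medium, because smoking coding, weights and smoker share are not visible.

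**What to change.** Before database lock, take the treatment difference, its p-value and the > 1 minute criterion from a model with treatment, period, actual sequence, smoking status and baseline sleep time as main effects and a random subject intercept. Fit the smoking and sleep-time interactions in a separate exploratory subgroup model.

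Alternatively, keep the SAP model and state that LS means use the observed smoking proportions and the mean of baseline sleep time. This stays closer to the protocol and also brings the SE back to 1.35. In either case, state how smoking status is coded, and make the same change in the log-scale analysis of SAP 6.1.3.2.

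The cost is about one sentence of SAP wording and, for the first option, one extra exploratory model. No new data are needed.

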6.1.3.1 Handling of missing values/censoring/discontinuations

If a subject has missing data at any time-point at night 1(2), then the missing observation will be imputed as average of observed values from nearest neighbourhood of that day.

Corporate Confidential Information

If all observations at a night are missing the values from other night will be used for MSLT evaluation.

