6.2 Secondary objectives

6.2.1 Variables

The secondary variable is MSLT at each time point (1:30, 3:30, 5:30 and 7:30) separately, averaged over two consecutive test nights.

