6.2.2 Descriptive analyses

MSLT

The secondary variable will be listed by treatment sequence, patient, period and time, and descriptive statistics will be provided, by treatment and time. Summary statistics will include mean (arithmetic and geometric), SD, CV (arithmetic and geometric), median, minimum, maximum.

An arithmetic mean +/- SD time profile (time-points: 1:30 AM, 3:30 AM, 5:30 AM, and 7:30 AM) plot will be provided for each treatment.

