6.2.3 Statistical model, assumptions and hypotheses

MSLT

A mixed model repeated measure (MMRM) analysis of variance model, will be performed over mean sleep latency test (MSLT) scores with treatment, actual treatment sequence, period, time-point, and treatment*time-point as fixed effects. A saturated covariance structure will be used for observations coming from same subject. If an unstructured covariance cannot be fitted simpler covariance structures will be examined.

The overall treatment effect for LML134 vs placebo will be reported along with a 95% CI.

A line graph of means of MSLT with 95% CI over time may be provided .

A supportive analysis with may be performed with additional covariates (total sleep time on actigraphy during baseline, key PSG parameters at baseline/screening) that may potentially affect individual mean MSLT data.

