6.2.3.1 Handling of missing values/censoring/discontinuations

Please refer section [6.1.3.1](#) .

Corporate Confidential Information

Corporate Confidential Information

7 Statistical methods for safety and tolerability data

All analysis will be performed under safety analysis set.

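### SAP 6.2.3.1 fills a missing nap in the time-point MSLT endpoint from other clock times of the same night, which blurs the time course that the endpoint is meant to show (minor)

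*SAP*

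**What the plan says.** SAP 6.2.1 defines the endpoint: "The secondary variable is MSLT at each time point (1:30, 3:30, 5:30 and 7:30) separately, averaged over two consecutive test nights". It serves the secondary objective on the time course of the effect (SAP 1.3.2).

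On missing data, SAP 6.2.3.1 shows no rule of its own, only a pointer ("Please refer section [6.1.3.1"). The rule it points to has two parts:

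- Single missing nap: "the missing observation will be imputed as average of observed values from nearest neighbourhood of that day".
- Whole night missing: "If all observations at a night are missing the values from other night will be used for MSLT evaluation".

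A redacted block stands between these two sentences.

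The model in SAP 6.2.3 includes "period, time-point, and treatment*time-point as fixed effects". The one model result it commits to is this: "The overall treatment effect for LML134 vs placebo will be reported along with a 95% CI". SAP 6.2.2 adds that "descriptive statistics will be provided, by treatment and time" and announces a plot ("An arithmetic mean +/- SD time profile"). It does not say whether these use filled or observed values.

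**The concern.** The single-nap rule sits under the primary endpoint, which averages all eight naps of a period. There, borrowing within a night does little. The secondary endpoint exists to keep the clock times apart, and a fill from neighbouring times mixes them again. Protocol 11.4.2 itself says that MSLT results depend on circadian rhythm and that compared values need time matching.

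The end naps are the most exposed. If the neighbourhood means adjacent naps, 1:30 and 7:30 have a neighbour on one side only. The 7:30 nap is 9.5 hours after dosing (night-time assessment table, Protocol 8.1). It falls in the commute window of Protocol 3.3 and near the end of the roughly 10 hours over which full efficacy is expected. A waning effect would show there, and a fill from 5:30 would partly hide it.

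The two parts of the SAP rule also differ in approach: a wholly missing night is replaced by clock time from the other night, a single nap is not.

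**Working it through.** **Plan figures.** The documents give no figure for this endpoint or for missing naps, and Protocol 11.8 reports no power analysis for secondary variables. Table 11-1 (Protocol 11.7) is used here only for scale.

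- SE with SD 4 and 36 subjects: 4 × √(2/36) = 0.943.
- Both criteria are met if the estimate exceeds max(1, 1.2816 × 0.943) = 1.208.
- At a true effect of 2.0 this gives 79.9% (stated 80.0%), and at 1.0 it gives 41.3% (stated 41.3%).
- The same reading with the 18 completers of SAP 1.4: 4 × √(2/18) = 1.33 min.

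**From the documents.** Four naps on each of two nights; score = mean of the two nights; donors from the same day.

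**Assumed.** Step between adjacent naps d = 1-3 min on a linear profile; share of 7:30 naps missing per night m = 5-20%; night-to-night difference n; donors are adjacent naps unless stated.

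**One subject, one 7:30 nap missing.**

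- Adjacent fill: error in the time-point score d/2 = 0.5-1.5 min.
- If the neighbourhood is the whole night, the donors lie d, 2d and 3d away (mean 2d), so the error is d = 1-3 min.
- Observed naps only: error n/2. This is the closer value when |n| < d (or < 2d for the whole-night reading).
- A missing middle nap, filled from both sides, has no error on a linear profile.

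**Treatment mean at 7:30.** Shift m × d, from 0.05 × 1 = 0.05 to 0.20 × 3 = 0.60 min.

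**Contrast at 7:30 (min).** The overall effect is taken as the mean of the four time-point contrasts. The observed-only column assumes missingness unrelated to latency and no night difference that varies by treatment.

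| Case | True 7:30 | Adjacent fill | Observed only | Overall effect |
|---|---|---|---|---|
| Equal missingness, constant effect 2 | 2.00 | 2.00 | 2.00 | unchanged |
| Missing in drug period only, m = 10%, constant effect 2 | 2.00 | moved by m × d = 0.10-0.30 | 2.00 | moved by 0.025-0.075 |
| Equal missingness, effects 2, 2, 2, 1 | 1.00 | (1 − m) × 1 + m × 2 = 1.05-1.20 | 1.00 | 1.75 becomes 1.76-1.80 |

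In the second case the direction depends on the slope and the size is proportional to m. In the third, the overall effect is 1.75 + m/4. A shift of 0.075 is 0.075/1.33 = 5.6% of the SE above.

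**Check by simulation.** 18 subjects, assumed effects 3, 2.5, 1.5 and 1 min, nap residual SD 3 min. The 7:30 effect (true 1.0) averages 1.05 and 1.10 under the fill at m = 10% and 20%, and 1.00 under the same-clock-time rule. At m = 20% the SE is 0.70 with complete data, 0.70 with the fill and 0.83 with the same-clock-time rule. The fill thus reports the precision of complete data.

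**Cost of observed-only.** With independent nap residuals, the variance of the 7:30 mean relative to complete data is (1 + 3m)/(1 + m) among subjects with a score. Dividing by (1 − m²) counts those missing both nights:

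- m = 5%: 1.095/0.9975 = 1.098, SE × 1.05
- m = 10%: 1.182/0.99 = 1.194, SE × 1.09
- m = 20%: 1.333/0.96 = 1.389, SE × 1.18

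If 10% of Night 2 naps are missing and n differs between treatments by 1-3 min, the observed-only contrast is off by 0.10 × (1 to 3)/2 = 0.05-0.15 min. The adjacent fill has no error from this source.

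**The case against.** The best defence is that same-night borrowing respects the night. Protocol 3.2 says MSLT can be strongly influenced by the preceding sleep. Night 2 follows a daytime sleep that itself comes after the first dose and is recorded by PSG to look for a drug effect (Protocol 8.6.7). The night difference could therefore vary by treatment, and a score from one night would carry it. This stands as a real cost of the fix. It does not justify filling a time-course endpoint from other times and counting the result as observed, and the SAP accepts other-night values when a whole night is missing.

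The redacted block may define or limit the neighbourhood. That also stands, but the visible words restrict donors to the same day, and there the only other post-dose naps are at other clock times.

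Missing naps may be rare, since testing is in-house and supervised. The endpoint is unpowered, in a non-confirmatory study that stopped after 18 completers. All of this limits the weight of the point.

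Three stronger readings are tempting and not supported:

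- *The by-time summaries and the profile plot are distorted.* The rule is a subsection of the model section, and SAP 6.2.2 does not say which values it uses. They are affected only if they use the filled data.
- *The SAP contradicts the protocol on this endpoint.* Protocol 11.5.1 sets no imputation rule for the time-point score. Protocol 11.4.3 and SAP 6.1.3.1 do differ for a single missing nap in the primary score, but that is a separate, smaller matter.
- *The drug-placebo contrast is biased in general.* With equal missingness and a constant effect it is unchanged.

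**Conclusion.** The point holds and is minor. The SAP applies a within-night fill to an endpoint defined separately by clock time, so one filled nap puts half of that subject's time-point score on other clock times. The whole score is borrowed only if the nap is missing on both nights. If donors are adjacent naps, the end-nap means shift wherever the profile slopes.

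The contrast at a clock time is biased only under unequal missingness or an effect that changes over the night. The second condition is what the time-course objective sets out to examine. In the cases worked, the 7:30 contrast is off by 0.05-0.30 min, and the overall MMRM effect by 0.075 min or less. These sizes rest on assumed missing rates and steps, because the documents give neither.

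**What to change.** Replace the cross-reference in SAP 6.2.3.1 with a rule of its own:

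> The time-point score uses observed naps only. If one night's nap is missing at a clock time, the other night's value at that clock time is the score. No value is imputed across clock times. A time point missing on both nights stays missing in the MMRM (assumed missing at random).

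State that the summaries and plot of SAP 6.2.2 use the same scores. Tabulate missing naps by treatment, night and clock time, so that a reader can see whether the rule mattered.

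This takes SAP wording, one derivation change and one count table before database lock, with no new data. The statistical price is the wider SE at 7:30 (about 5-18% at 5-20% missing) and exposure to any night-to-night difference, both sized above.
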